4 STUDY DESIGN

This is a prospective, single-arm, multi-center post-market observational study to assess the performance of the Pipeline™ Flex Embolization Device with Shield Technology™ in subjects undergoing treatment for intracranial aneurysms.

4.1 Expected Duration of the Study and Subject Participation.

Up to 200 subjects who meet the Inclusion/Exclusion Criteria may be enrolled over a period of approximately 2 years to reach a target number of subjects. Study participation includes initial screening and baseline evaluation, treatment using the Pipeline™ Flex Embolization Device with Shield Technology™, and follow-up visits at the discretion of the treating physician for 1 year beyond the index procedure. The total study duration is expected to be approximately 3 years.

4.2 Number of Sites and Subjects

Up to 200 subjects at up to 25 sites worldwide may participate. Each participating investigational site should attempt to enroll at least 1 subject and will be allowed to enroll up to 30 subjects who meet all study eligibility criteria.

4.3 Study Population

The study population will consist of subjects who have an intracranial aneurysm and are enrolled in the study. The treated aneurysm may be ruptured (with a Hunt and Hess grade of ≤ 3) provided that the Pipeline™ Flex Embolization Device with Shield Technology™ is used according to its Instructions for Use and its intended use during the treatment regimen.

For subjects with more than one aneurysm requiring treatment, the following guidance is to be followed for subjects to be enrolled in the study.

- If more than one aneurysm can be covered by a single Pipeline device or two overlapped devices, the multiple aneurysms treated by that device(s) may all be included in the study. A maximum of two overlapped devices in consecutive arterial segments will be permitted. The largest aneurysm meeting criteria will be designated the target aneurysm. For equal sized aneurysms, the Core Lab will designate the target aneurysm.
- If the subject has more than one aneurysm and all aneurysms requiring treatment cannot be covered by a single Pipeline device or two overlapped devices, the non-target aneurysms should be treated first. After waiting at least 30 days per exclusion criterion #1 below, the subject may return for Pipeline treatment of the target aneurysm.

4.3.1 Inclusion Criteria

Subjects must meet all of the following general inclusion criteria:

1. Subject has provided written DRF or informed consent using the IRB/EC-approved consent form and agrees to comply with protocol requirements.
2. At least 18 years of age.
3. Subject has already been selected for flow diversion therapy as the appropriate treatment.

4. Subject has a target IA that has a parent vessel with diameter 1.5-5.0 mm distal/proximal to the target IA.

4.3.2 Exclusion Criteria

The subject must not meet any of the following general exclusion criteria:

1. Major surgery including endovascular procedures within the past 30 days.
2. Subject with target IA located in the basilar artery.
3. Subject with anatomy not appropriate for endovascular treatment due to severe intracranial vessel tortuosity or stenosis determined from baseline or pre-procedure imaging, or a history of intracranial vasospasm not responsive to medical therapy.
4. Stent is in place in the parent artery at the target IA location.
5. Subject with an acutely (within 30 days) ruptured aneurysm with a Hunt and Hess grade of 4 or higher.
6. Any known contraindication to treatment with the Pipeline™ Flex Embolization Device with Shield Technology™ per Instructions for Use.
7. The investigator determines that the health of the subject or the validity of the study outcomes (e.g., high risk of neurologic events, conditions that may increase the chance of stroke, worsening of clinical condition in the last 30 days) may be compromised by the subject's enrollment.
8. Pregnant or breast-feeding women or women who wish to become pregnant during the length of study participation.
9. Subject is currently enrolled or planning to participate in a potentially confounding drug or device trial during the course of this study. Co-enrollment in concurrent trials is only allowed when documented pre-approval is obtained from Medtronic.
10. Legal incapacity or evidence that a subject cannot understand the purpose and risks of the study or inability to comply fully with study procedures.

4.3.3 Point of Enrollment

Given that the prospective study population consists of patients who are already selected for flow diversion therapy and that the screening assessments consist of standard patient diagnostics for this therapy, subjects are considered enrolled in the study once the subject has signed and dated the Informed Consent or DRF and the Pipeline™ Flex Embolization Device with Shield Technology™ is advanced into the micro catheter inside the subject.

5 STUDY PROCEDURES

5.1 Patient information process

Patient informed consent will be obtained in accordance with local laws and regulations. Whether to use an Informed Consent or Data Release Form (DRF) is dependent on local regulatory requirements and local EC/IRB requirements, if applicable. The strictest requirement will be applied. The Informed Consent or DRF must be approved by the sponsor and the Site's EC/IRB, if applicable.

Legally incompetent or unconscious subjects are not expected to be included in this study.

5.2 Informed Consent process

A thorough explanation will be provided to the subject (or legally authorized representative) as to the nature and objectives of this study. Details of the study should include (but are not limited to) the following terms:

- Purpose of the study
- Participation is voluntary, and there is no penalty for withdrawal
- Potential risks/benefits for participation
- Contact information to ask questions or voice concerns

The study investigator and/or staff are responsible for obtaining written informed consent from each potential subject. Informed consent should be obtained in written format and using a form approved by the local IRB/EC, if applicable. The form should contain standard language consistent with local policies for ensuring privacy of confidential information. All subjects must sign the informed consent prior to any procedures/tests that go beyond initial assessments associated with the standard care for subjects with intracranial aneurysms and before any study related treatment assessments are administered and subject-related health information can be entered into the study database.

It is the responsibility of the investigator to give each subject (or subject's legally authorized representative) prior to inclusion in the study, full and adequate verbal and written information regarding the objective of this study and the confidentiality of the data collected.

The Sponsor will inform the investigators whenever information becomes available that may be relevant to the subject's confirmed participation in the clinical study. The investigator or his/her authorized designee should inform the subject in a timely manner. The Sponsor will revise the written Informed Consent Form whenever new information becomes available that may be relevant to the subject's confirmed participation in the clinical study. The revised information will be sent to the investigator for approval by the EC/IRB, if applicable, and a copy of this information must be provided to the participating subjects.

After all persons have signed and dated the informed consent, the investigator must provide the subject with a copy of the signed and dated informed consent.

5.3 Data Release Form process

The investigator must obtain written DRF prior to releasing personal information of the subject.

During the consent discussion the investigator or his/her designee must fully inform the subject of the study in non-technical wording understandable for the subject.

The subject must have ample time and opportunity to inquire about details of the study, and to decide whether or not to participate in the clinical study. All questions about the study should be answered to the satisfaction of the subject.

When the subject decides to participate in the clinical study, the written DRF must be signed and personally dated by the subject and the investigator.

After all persons have signed and dated the DRF the investigator must provide the subject with a copy of the signed and dated DRF.

5.4 Procedure

The Pipeline™ Flex Embolization Device with Shield Technology™ placement procedure is described in detail in the Instructions for Use (IFU) document. The investigator should review and understand the complete IFU prior to performing any Pipeline™ Flex Embolization Device with Shield Technology™ placement in this clinical study.

Recommendations: In addition to the Pipeline™ Flex Embolization Device with Shield Technology™ (study device), the following devices and equipment are recommended during the study procedure.

- A tri-axial system
- 0.027 microcatheter
- Navien support catheter
- Long sheath (minimum of 90 cm)

No other devices or concomitant medications different from clinical practice have to be used during the SHIELD Study, since this is a post-market non-interventional study.

5.5 Data Collection

Eligible subjects will be treated with the Pipeline™ Flex Embolization Device with Shield Technology™.

Subjects will undergo standard of care follow-up visits. Data generated per standard of care will be collected for 1 year (± 8 weeks) beyond the index procedure. All follow-up visits and telephone calls during this time period will be recorded. A summary of the data to be collected is listed in **Table 5-1**.

In order to track compliance with antiplatelet therapy, subjects will be contacted at a minimum of approximately (± 14 days), 3 (± 30 days), 6 (± 6 weeks), and 12 (± 8 weeks) months post-index procedure and asked to confirm their current antiplatelet regimen and that all relevant adverse events (**Section 6**) have been reported.

A survey will be administered to all centers to collect their standard antiplatelet therapy regimen at the start of the study and annually.

Table 5-1. Data Collection

Time Period	Data to be Collected
Baseline	
• Relevant medical history and demographics• Aneurysm characteristics, symptoms and status (ruptured or unruptured)• Hunt & Hess Grade and WFNS (if ruptured)• Antiplatelet medication use within past 30 days• Other relevant concomitant medications• Platelet reactivity testing• NIH Stroke Scale (NIHSS)• Modified Rankin Scale (mRS)
Procedure	
• Relevant medications including antiplatelet regimen• Adverse events• Platelet reactivity testing• Procedure and fluoroscopy times• Study device information including side branches covered• Concomitant treatments• Deployment success at target IA• Imaging to be sent to the Core Lab*• Aneurysm occlusion• NIHSS• mRS
Post-Implant Follow-up	
• Relevant medications including antiplatelet regimen• Adverse events• Platelet reactivity testing• Imaging to be sent to the Core Lab*• Aneurysm occlusion• Retreatment• NIHSS• mRS

*All imaging taken (e.g., angiograms, CT, MR, rotational angiography with 3D reconstruction, cone-beam CT, etc.) should be provided to the Core Lab.

5.6 Screen Failure

Subject will be considered a screen failure if:

- The subject signs the informed consent or DRF but fails to meet study inclusion/exclusion criteria during the screening and baseline phase.
- The subject signs the informed consent or DRF, meets the study inclusion/exclusion criteria but an attempt to implant the Pipeline™ Flex Embolization Device with Shield Technology™ is not performed.

Subjects that undergo consent but are screen failures will be exited from the study and will not be required to undergo any additional follow-up. Only the reason for subject screen failure will be recorded.

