6 ADVERSE EVENTS

The following Adverse events will be collected during the course of the study on the eCRFs.

- All Adverse Events (AE) with an underlying neurological cause (Neurological Adverse Events)
- All Device Related Adverse Effects
- All Procedure Related Adverse Events
- All Bleeding Events
- All Serious Adverse Events (SAEs)

Adverse event status will be evaluated throughout the study. These will include events occurring from the point of enrollment until a subject exits the study. If the subject is enrolled and the study procedure is attempted, but the Pipeline™ Flex Embolization Device with Shield Technology™ is not implanted for any reason, subjects will be followed to discharge and relevant safety events will be collected. Investigators must obtain all information available to determine the causality and outcome of the AE and to assess whether it meets the criteria for classification as a serious and/or

unexpected event requiring notification to the Sponsor, and, where applicable, regulatory agency and IRB/EC, within the specified reporting timeframe. AEs will be categorized using the definitions in **Section 6.1**.

All study AEs, as well as the treatment and follow-up required, should be documented in the subject's medical records and in the eCRF. All study SAEs that occur during the 1 year follow-up period will be followed by the investigator until resolution or until 30 days after the occurrence of that event. A list of potential anticipated adverse events is provided in **Section 10.2**.

Bleeding events will be captured as Adverse Events by the sites and will be graded according to the GUSTO⁴⁴ bleeding criteria as seen in

Table 6-1 by the Clinical Events Committee.

Table 6-1. GUSTO Bleeding Criteria

GUSTO Bleeding Category	Definition
Severe or Life-Threatening	Intracerebral hemorrhage Substantial hemodynamic compromise requiring treatment
Moderate	Requiring blood transfusion but not resulting in hemodynamic compromise
Mild	Bleeding that does not meet the above criteria

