Subjects will be considered enrolled in the study once the patient has signed and dated the Informed Consent or DRF and the Pipeline™ Flex Embolization Device with Shield Technology™ is advanced into the micro catheter inside the patient. Per each site’s standard of care procedure, at screening, each patient can undergo a neurologic examination and assessment using the mRS and NIHSS, blood draw for hematocrit, platelet count, platelet function testing, serum creatinine, and a pregnancy test (if applicable). Pertinent medications taken by the study participant starting on the day of study procedure were collected while for platelet reactivity start date can also be > 30 days before procedure (in case patient was already under antiplatelet, including anticoagulants and antiplatelet therapy). Subjects will be assessed and documented at baseline. Patient eligibility assessment is to be performed based on data available to the investigator at the time of screening. Patient will be considered a screen failure if:

- The patient signs the informed consent or DRF but fails to meet study inclusion/exclusion criteria during the screening and baseline phase.
- The patient signs the informed consent or DRF, meets the study inclusion/exclusion criteria but an attempt to implant the Pipeline™ Flex Embolization Device with Shield Technology™ is not performed.

The investigator will assess device occlusion, device placement and overall status of the aneurysm. At the investigator’s discretion, the target IA may be retreated at any time during the study. In such situations, the date of the initial procedure (and not the date of the retreatment) will be considered Day 0.

If the target IA undergoes an attempted deployment with the Pipeline™ device with Shield Technology™ but is not implanted or receives an alternate treatment (e.g., coils), the patient is considered an implant failure and will be followed up until hospital discharge. However, if the target IA does not undergo an attempted deployment with the Pipeline™ device with Shield Technology™ and is not treated or receives an alternate treatment (e.g., coils) during the initial procedure, the patient is considered a screen failure and no further follow up is required.

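### An enrolled subject in whom the device is advanced but deployment is not attempted falls under conflicting collection rules and drops out of the safety tables

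*Protocol*

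**What the plan says.** **Enrollment.** Under Protocol 4.3.3 a subject is enrolled once consent or the data release form is signed and the device "is advanced into the micro catheter inside the subject". The SAP repeats this in sections 3 and 5.

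**Screen failure.** Protocol 5.6 counts as a screen failure a consented, eligible subject for whom "an attempt to implant the Pipeline™ Flex Embolization Device with Shield Technology™ is not performed". Such subjects "will be exited from the study and will not be required to undergo any additional follow-up", and "Only the reason for subject screen failure will be recorded". The rule is not limited to subjects who are not yet enrolled. SAP section 5 (Study Procedure) draws the line at attempted deployment: without one, "the patient is considered a screen failure and no further follow up is required".

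**ITT.** The ITT entry in SAP section 2 foresees a device that does not reach the target, so that the operator does not try to deploy it. It removes that subject from ITT and calls the event rare.

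**Adverse events.** Protocol 6 says of the events to be collected: "These will include events occurring from the point of enrollment until a subject exits the study". For an enrolled subject whose procedure is attempted, it adds that if the device "is not implanted for any reason, subjects will be followed to discharge and relevant safety events will be collected".

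**Reporting.** SAP 7.10 bases the adverse event summaries primarily on ITT, and later on ITT and the ICA population. SAP 7.9 makes ITT the primary population for the endpoints, including major stroke or neurological death at 1 year.

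**The concern.** An enrolled subject whose procedure stops after the device is advanced but before deployment is attempted is subject to two rules that cannot both be followed. One ends participation and, in Protocol 5.6, keeps only a reason. The other collects safety events to discharge.

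This matters because the reason for stopping may be the complication itself. If a vessel is perforated or a thromboembolic stroke occurs while the device is being advanced, the operator may abandon the deployment. Whether the subject counts then depends partly on the outcome that the study is meant to measure. The quantities exposed are the adverse event tables, the secondary endpoint of major stroke or neurological death at 30 days, and the primary safety endpoint at 1 year. SAP section 6 examines the last against 15%, and SAP section 3 says that the data may be used for a US indication evaluation.

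**Working it through.** The documents give no figure for this group, so there is none to reproduce. The check has two parts: tracing one subject through the rules, and an illustration of size.

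**1. One subject through the rules.** Consent is signed, the device is advanced into the microcatheter, it does not reach the target, and deployment is not attempted.

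- Protocol 4.3.3: enrolled.
- SAP section 5, Study Procedure: screen failure, no further follow-up.
- Protocol 5.6: screen failure with only the reason kept, if an attempt to implant means an attempted deployment. Protocol 9.3 lists being enrolled, undergoing the procedure and having an implant attempt as separate conditions, which favors that reading without settling it.
- Protocol 6: within the collection window and, as enrolled without an implant, followed to discharge.
- SAP section 2: not in ITT. FAS, ICA and non-ICA are all subsets of ITT (SAP section 5, Analysis Populations), so no defined population contains this subject.

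The last step holds whichever collection rule a site follows.

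**2. Direction.** Let *m* be the number of excluded subjects, *e* the events among them, and *x* the events among the other *n*. The reported rate is *x/n* and the full rate is (*x*+*e*)/(*n*+*m*). The full rate is higher exactly when *e/m* > *x/n*. The event count can only fall through exclusion, but the rate can move either way.

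**3. Size, 200 enrolled in all.** Assumed: *m* = 2 to 6, *e* = 1 to 2, *x* = 12.

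| m | e | All enrolled | Excluding them | Understatement (points) |
|---|---|---|---|---|
| 2 | 1 | 13/200 = 6.5% | 12/198 = 6.06% | 0.44 |
| 2 | 2 | 14/200 = 7.0% | 12/198 = 6.06% | 0.94 |
| 4 | 2 | 14/200 = 7.0% | 12/196 = 6.12% | 0.88 |
| 6 | 1 | 13/200 = 6.5% | 12/194 = 6.19% | 0.31 |
| 6 | 2 | 14/200 = 7.0% | 12/194 = 6.19% | 0.81 |
| 6 | 0 | 12/200 = 6.0% | 12/194 = 6.19% | −0.19 |

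The range is about 0.3 to 0.9 point when there is at least one event. With none, exclusion raises the rate by about 0.2 point.

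**4. Against the 15% threshold.** SAP section 6 uses a two-sided 95% Clopper-Pearson interval, whose upper limit is the 97.5% quantile of Beta(*x*+1, *n*−*x*). Here 200 is the ITT size, as SAP section 5 intends, and excluded subjects are added to it.

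- 19/200 = 9.5%: upper limit 14.44%.
- 20/200 = 10.0%: upper limit 15.02%.
- 19/200 plus two excluded subjects, both with events: 21/202 = 10.4%, upper limit 15.45%.
- 11/200 = 5.5%, upper limit 9.63%; adding four subjects with two events gives 13/204 = 6.37%, upper limit 10.65%.

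The reading against 15% changes only when the observed rate is already near 9.5 to 10%.

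**The case against.** The strongest reply is that the Protocol can be read as consistent with itself. Protocol 5.6 never mentions deployment, and it does not define an attempt to implant. If advancing the device already counts as an attempt, 5.6 covers only subjects in whom it was never advanced, and Protocol 6 covers the rest. That reading is available, and it is why the conflict rests first on SAP sections 2 and 5, which do use deployment as the line, set against Protocol 6.

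A reader might infer that these events are never collected. The documents do not support that. Protocol 6 requires adverse events from enrollment, Table 5-1 lists adverse events at the procedure, and Protocol 6.2 requires serious events to be reported within 24 hours. SAP section 5 waives further follow-up; it does not say that procedural events go unrecorded. Loss at collection therefore occurs only where a site puts 5.6 or SAP section 5 ahead of these rules.

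A reader might also infer that exclusion can only lower the safety rate. It cannot be put that strongly, because the denominator shrinks too.

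Finally, the assumed counts imply event rates of 1/6 = 17% to 2/2 = 100% in aborted cases, against about 6% in the rest, and nothing in the documents supports those figures. That stands: the table shows a scale and is not an estimate.

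What the reply does not remove is the reporting gap. SAP 7.10 says that summaries are not limited to ITT, but the SAP defines no population that would hold these subjects.

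**Conclusion.** The inconsistency is real and should be corrected. Sites have conflicting instructions for an enrolled, device-exposed subject without an attempted deployment. Events in these subjects fall outside the planned adverse event summaries and the primary safety endpoint even when they are collected. The event count can only fall; the rate is understated if aborted subjects have a higher event rate than the rest, which is plausible because a complication can be the cause of stopping.

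The likely effect is small: about 0.3 to 0.9 percentage point under the assumed counts, in the other direction by about 0.2 point if six aborted subjects have no events, and decisive against 15% only at an observed rate near 9.5 to 10%. All of this rests on assumed counts for a group that the SAP describes as rare. The documents do not support a claim that the safety result is materially biased.

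**What to change.** - In Protocol 5.6 and SAP section 5, limit screen failure to subjects in whom the device was never advanced into the microcatheter, that is, before enrollment. Define what an attempt to implant means.
- Apply the existing Protocol 6 collection rule to every enrolled subject.
- Report the adverse event tables and the major stroke or neurological death endpoint on all enrolled subjects, alongside or in place of the attempted-deployment ITT set. This needs matching edits to Protocol 9.3, the ITT definitions in SAP sections 2, 5 and 7.1.3, and SAP 7.10. Without them the recovered events stay out of the tables.
- State that follow-up of subjects without an implant ends at discharge, so that their later status to 1 year is missing. An event before discharge counts. For those without one, SAP 7.4 already provides multiple imputation and a separate observed-data tabulation; report both, since the imputation would draw mainly on implanted subjects.

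The cost is a set of wording changes and in-hospital adverse event forms for a few subjects. Implant failures are already followed to discharge, so the process exists. The safety rate may become slightly less favorable.
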